Least squares means and their standard errors for change in MADRS total score based on the MMRM analysis will be plotted by treatment group and visit. Mean treatment difference (raw mean difference \pm standard error) in change in primary endpoint between each cariprazine dose and placebo with missing values imputed using the LOCF approach will be plotted against country. In addition, summary statistics will be provided by center to examine the consistency of treatment effect across the study centers. The impact of dropouts on the efficacy outcomes will be explored graphically by plotting the time courses of mean changes by dropout reason.

To compare with historic studies, the LOCF approach will be used with an ANCOVA model that has treatment group, pooled country and ADT failure category (per CRF) as factors and the baseline value as the covariate. Results of analyses from MMRM and from ANCOVA models will also be reported for each visit between baseline and Week 6.

To determine whether the treatment effect is consistent across various subgroups, the estimate of the between-group treatment effect (with a 95% CI) for each cariprazine dose versus placebo for the primary efficacy variable will be estimated within each category of the following classification variables:

- ADT failure category (one ADT failure, more than one ADT failure)
- Region (US, Non-US)

The treatment effect within each category of a subgroup factor will be assessed using MMRM with terms including treatment group, visit, and treatment group-by-visit interaction, the baseline value and baseline-by-visit interaction, in addition to one term defined as following:

- Add term ADT failure category while conducting region subgroup analyses
- Add term Country while conducting ADT failure category subgroup analyses.

Treatment effects and nominal 95% CI by category for the classification variables listed above will be reported. Because the sample size for a specific subgroup category might be small, the MMRM might not converge, in which case only summary statistics using the LOCF data at Week 6 will be reported.

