6.2.2.3 Clinical Global Impressions–Improvement

The Clinical Global Impressions–Improvement (CGI-I) scale ([Guy 1976](#)) is a clinician-rated scale that in this study will be used to rate total improvement or worsening of mental illness from Visit 2, regardless of whether the investigator considers it to be a result of drug treatment or not. The patient will be rated on a scale from 1 to 7, with 1 indicating that the patient is very much improved and 7 indicating that the patient is very much worse. The

CGI-I will be administered by an investigator, subinvestigator or rater with extensive professional training and experience in assessing mental illness.

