7.3 Hypothesis and Methods of Analysis

All efficacy analyses will be based on the mITT population. Baseline for efficacy is defined as the last nonmissing efficacy assessment before the date of the first dose of DB IP. All statistical hypothesis tests will be 2-sided 5%-level of significance tests for main effects. All confidence intervals (CIs) will be 2-sided 95% CIs, unless stated otherwise.

To compare with historic studies, some analyses based on the imputed data using the last-observation-carried-forward (LOCF) approach, will be presented for all efficacy parameters. Only the postbaseline total score of a parameter will be imputed; individual item scores will not be carried forward. The baseline value will be carried forward only for the intermittent missing values immediately after baseline. If all the postbaseline values are missing, the baseline value will not be carried forward.

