Dosing compliance for the background ADT during a specified period is defined as the dose actually taken by a participant during that period divided by the dose expected to be taken during the same period multiplied by 100. Descriptive statistics for ADT compliance will be presented for each ADT and overall by the double-blind investigational product treatment group for the period from the first dose of DB IP actually taken to the last dose of DB IP actually taken for the Safety Population.

9.0 **EFFICACY ANALYSES**

All efficacy analyses will be based on the mITT population. Baseline for efficacy is defined as the last non-missing efficacy assessment before the date of the first dose of DB IP. All statistical tests will be conducted at the $\alpha=0.05$ (2-sided) level for main effects. All confidence intervals (CIs) will be 2-sided 95% CIs, unless stated otherwise.

For efficacy analyses in which country is a factor, a *small country* will be defined as a country with fewer than 2 participants in at least one treatment group in the mITT Population. Small countries will be pooled to form pseudo-countries so that each treatment group includes at least 2 mITT participants within the country. Countries will be ranked on number of participants that are part of the mITT Population and lowest ranked countries will be pooled (sequentially, i.e., a new ranking is made after each step) until the smallest pooled country has reached at least 2 participants in each treatment group.

To compare with historic studies, some analyses based on the imputed data using the last-observation-carried-forward (LOCF) approach, will be presented for all efficacy parameters. Only the postbaseline total score of a parameter will be imputed; individual item scores will not be carried forward. The baseline value will be carried forward only for the intermittent missing values immediately after baseline. If all the postbaseline values are missing, the baseline value will not be carried forward.

9.1 **PRIMARY EFFICACY PARAMETER**

The primary estimand is provided below through specification of the population, the variable, the handling of intercurrent events, and the population-level summary.

Population

The target population are participants with MDD who have had an inadequate response to antidepressant therapy in the current episode and who satisfy the inclusion and exclusion criteria as specified in the protocol.

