9.2 KEY SECONDARY EFFICACY PARAMETER

The key secondary endpoint is the change from baseline to Week 6 in the CGI-S score.

To test the secondary hypotheses that each dose of cariprazine is superior to placebo in the reduction of CGI-S score after 6 weeks of treatment, the change from baseline in CGI-S score will be analyzed using the MMRM approach similar to the one used for the primary analysis. A sensitivity analysis will also be performed using ANCOVA (with LOCF imputation) as used for the analysis of primary endpoint.

To control the overall familywise type I error rate at the 0.025 level (one-sided), a truncated Hochberg will be used for the primary endpoint, and the regular Hochberg procedure for the key secondary endpoint. The truncation parameter will be set to $\gamma = 0.9$ (Dmitrienko 2011).

The cariprazine dose groups will be labeled as Dose 1 (1.5 mg) and Dose 2 (3.0 mg).

The null hypotheses can be grouped into two families:

- (i) Family 1 includes the null hypotheses H_1 and H_2 for the primary endpoint:

H_1 denotes the null hypothesis of the difference in mean change from baseline in MADRS at Week 6 between cariprazine Dose 1 and placebo is ≥ 0 .

H_2 denotes the null hypothesis of the difference in mean change from baseline in MADRS at Week 6 between cariprazine Dose 2 and placebo is ≥ 0 .

- (ii) Family 2 includes the null hypotheses H_3 and H_4 for the key secondary endpoint:

H_3 denotes the null hypotheses of the difference in mean change from baseline in CGI-S at Week 6 between cariprazine Dose 1 and placebo is ≥ 0 .

H_4 denotes the null hypotheses of the difference in mean change from baseline in CGI-S at Week 6 between cariprazine Dose 2 and placebo is ≥ 0 .

The gatekeeping procedure utilizes the following decision rules:

- (i) Step 1. The null hypotheses in Family 1 are tested using the truncated Hochberg procedure at the full α level. Let $p_{(1)} < p_{(2)}$ denote the ordered p-values in Family 1 and let $H_{(1)}$ and $H_{(2)}$ denote the associated null hypotheses. The truncated Hochberg procedure rejects both $H_{(1)}$ and $H_{(2)}$ if $p_{(2)} \leq \alpha(1 + \gamma)/2$ or it rejects only $H_{(1)}$ if $p_{(1)} \leq \alpha/2$ and $p_{(2)} > \alpha(1 + \gamma)/2$.
- (ii) Step 2. The null hypotheses in Family 2 are tested as follows:

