The safety analysis will be performed using the safety population for the double-blind treatment period and safety follow-up period. The double-blind treatment period starts with the first dose of double-blind investigational product and ends with the last scheduled assessment at Visit 6 (Week 6) or early termination (before Week 6). The safety follow-up period starts the day after the last scheduled assessment at Visit 6 (or early termination) and ends with the last safety follow-up visit. The safety parameters will include adverse events (AEs), clinical laboratory parameters, vital signs, electrocardiogram (ECG) parameters, EPS scales, the C-SSRS and the YMRS. For each safety parameter, the last assessment made before the first dose of double-blind investigational product will be used as the baseline for all analyses of that safety parameter. The summarization will be by treatment group for both double-blind and safety follow-up periods. Continuous variables will be summarized by number of participants and mean, SD, median, minimum, and maximum values. Categorical variables will be summarized by number and percentage of participants.

10.1 **ADVERSE EVENTS**

Adverse events will be coded by system organ class and preferred term using the *Medical Dictionary for Regulatory Activities*, version 24.0.

An adverse event (AE) will be considered a treatment-emergent adverse event (TEAE) if the AE began or worsened (increased in severity or became serious) on or after the first dose of DB investigational product. Per case report form instructions, a new AE record will be created with a new AE onset date for any AE that worsens. Therefore, TEAEs can simply be identified as those AEs with recorded onset date (and time, if known) on or after the date of the first dose of study intervention.

An AE will be considered a TESAE if it is a TEAE that additionally meets any SAE criterion.

For the DB treatment period, the number and percentage of participants reporting TEAEs in each treatment group will be tabulated by system organ class and preferred term; by system organ class, preferred term, and severity; and by system organ class, preferred term, and relationship to the IP. If more than 1 AE is coded to the same preferred term for the same participant, the participant will be counted only once for that preferred term using the most severe and most related occurrence for the summarization by severity and by relationship to the IP.

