15.0 DATA HANDLING CONVENTIONS

15.1 VISIT TIME WINDOWS

Table 15-1 presents the visits assigned for efficacy and safety analyses and the corresponding range of treatment days (window) during which an actual visit may occur.

Table 15-1 Efficacy and Safety Analysis Visit Definitions

Analysis Phase	Derived Visit	Scheduled Visit Day ^a	Window
Pretreatment	Baseline	Day 1	Days ≤ 1
Double-blind Treatment	Week 1	Day 8	Days [2, 11]
	Week 2	Day 15	Days [12, 21]
	Week 4	Day 29	Days [22, 35]
	Week 6	Day 43	Days ≥ 36 and within Double-blind Treatment Period
	End of Double-Blind Treatment Period ^b	Final double-blind treatment visit (expected Day 43) or ET visit during the double-blind treatment period	Final non-missing assessment during the double-blind treatment period
Safety Follow-up	Week 10	Day 71	day of final double-blind or ET visit during the double-blind treatment period $+1 \leq \text{Days} \leq \text{last visit}$

a Relative to the date of the first dose of double-blind investigational product. Day 1 = the date of the first dose of double-blind investigational product.

b Presented in analysis tables for safety parameters, including but not limited to electrocardiograms, clinical laboratory values, and vital signs.

ET = early termination.

If the visit date is on or after the date of the first dose of double-blind investigational product, the study day is calculated by visit date – date of the first dose of double-blind investigational product + 1. If the visit date is before the date of the first dose of double-blind investigational product, the study day is calculated by visit date – date of the first dose of double-blind investigational product. Therefore, a negative day indicates a day before the start of the double-blind investigational product.

If a participant has 2 or more visits within the same window, the last visit with a non-missing value will be used for analysis.

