15.3 REPEATED OR UNSCHEDULED ASSESSMENTS OF SAFETY PARAMETERS

If a participant has repeated assessments before the start of the first treatment, the results from the final non-missing assessment made prior to the start of the DB investigational product will be used as baseline. If end-of-study assessments are repeated or if unscheduled visits occur, the last non-missing postbaseline assessment will be used as the end-of-study assessment for generating summary statistics. However, all postbaseline assessments will be used for PCS value determinations, and all assessments will be presented in the data listings.

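### SAP 9.0 and Protocol 7.3 place the efficacy baseline before the date of first dose; SAP Table 15-1 includes that date, so patients dosed on the Visit 2 date have two different baselines

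*SAP*

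**What the plan says.** The efficacy rule appears in both documents in almost the same words. SAP 9.0: "Baseline for efficacy is defined as the last non-missing efficacy assessment before the date of the first dose of DB IP". Protocol 7.3: "Baseline for efficacy is defined as the last nonmissing efficacy assessment before the date of the first dose of DB IP". Both tie baseline to the date of the dose, not to the dose itself.

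SAP 15.1 gives a second rule. Table 15-1 is titled as covering efficacy and safety visits. Its Baseline row is scheduled on Day 1 and takes every day up to and including Day 1. Footnote a defines the anchor: "Day 1 = the date of the first dose of double-blind investigational product". Ties within a window go to the later rating: "If a participant has 2 or more visits within the same window, the last visit with a non-missing value will be used for analysis".

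The safety rules in the same SAP use the dose, not its date. SAP 10.0: "the last assessment made before the first dose of double-blind investigational product will be used as the baseline". SAP 15.3, which is limited to safety parameters: "the final non-missing assessment made prior to the start of the DB investigational product will be used as baseline".

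Neither the list of changes in SAP 17.0 nor the amendment summary in SAP Appendix III mentions the difference.

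**The concern.** A rating made on the first-dose date is excluded by SAP 9.0 and included by Table 15-1, and nothing says which prevails. Protocol Section 3 has dosing start at Visit 2, and both schedules put Visit 2 on Study Day 1, so same-day dosing is a planned case.

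The SAP 9.0 sentence supplies both the response and the covariate for the primary endpoint, MADRS change at Week 6. It does the same for the key secondary: "The key secondary endpoint is the change from baseline to Week 6 in the CGI-S score". Two programmers following different sections could build different baseline datasets from one plan.

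The word *date* cannot be dismissed as loose drafting. SAP 7.0 uses the same phrase to separate prior medication (before the first-dose date) from concomitant medication (on or after it), and there it does exclude the dosing day.

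**Working it through.** The point concerns a definition, so the check applies both rules to the same patient.

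**Inputs**
- Study day (SAP 15.1): visit date minus first-dose date, plus 1 if the visit is on or after the first-dose date. There is no Day 0.
- Screening ratings (Protocol 8.4.1): MADRS, HAMD-17 and CGI-S, but no HAM-A.
- Visit 2 ratings (Protocol 8.4.2): MADRS, HAMD-17, HAM-A and CGI-S.
- Gap from Screening to Visit 2: up to 14 days, or 21 with sponsor approval (Protocol Table 1).

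**Result by timing of first dose**

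| First dose | Study day of Visit 2 | SAP 9.0 / Protocol 7.3 | SAP Table 15-1 |
|---|---|---|---|
| Same date as Visit 2 | 0 + 1 = 1 | Screening for MADRS, CGI-S, HAMD-17; none for HAM-A | Visit 2 for all four |
| 1 day later | −1 | Visit 2 | Visit 2 |
| 2 days later | −2 | Visit 2 | Visit 2 |

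So the rules part exactly when the first dose falls on the Visit 2 date.

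**What follows for such a patient under the literal SAP 9.0 rule**
- The Visit 2 rating enters no analysis. It is not baseline, and the Week 1 window opens only at Day 2.
- If MADRS falls by *d* points from Visit 1 to Visit 2, the patient's improvement from baseline is *d* points larger. The 50% responder cutoff is 0.5 × baseline, so it rises by 0.5 × *d*. A 1-point fall therefore adds 1 point of change and moves the cutoff by 0.5 point.
- HAM-A change and HAM-A response (SAP 9.3) cannot be computed. The HAM-A remission model also loses the patient, because it takes the baseline score as an explanatory variable.
- CGI-I keeps Visit 2 as its reference, since Protocol 6.2.2.3 uses it to "rate total improvement or worsening of mental illness from Visit 2". CGI-I and the change scores would then be measured from different visits.

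**Effect on the treatment comparison.** Screening and Visit 2 ratings both precede dosing. With baseline and baseline-by-visit in the MMRM, choosing one or the other changes the covariate, not the Week 6 score being compared. Under blinding there is no reason for the share dosed on the Visit 2 date to differ by arm. The adjusted MADRS difference is therefore unbiased under either rule.

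**Effect on the planning figures.** The stated power uses an effect size of 0.286, 15% dropout and a within-person correlation of 0.58; the baseline rule is not an input. With an effective 250 × (1 − 0.15 × (1 − 0.58²)) = 225.1 patients per arm, simulation gives 84.1% per dose under Hochberg (Protocol 7.7 states 84%) and 83.7% under the truncated procedure (SAP 13.0 states 83%). Power for at least one dose is 91.2% and 91.1%, against about 90% stated. These figures do not change.

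**The case against.** The best reply is that the documents nearly settle the matter. Table 15-1 is the operational visit-assignment rule, and it selects Visit 2. That visit is labelled Baseline throughout, CGI-I is rated from it, and HAM-A change is planned although HAM-A is first rated there. A reading that leaves same-day patients without a HAM-A baseline is not one that anyone would choose to program. This stands as evidence of intent, and it keeps the point small. It does not remove the contradiction, because the section that expressly defines the efficacy baseline says something else and so does the protocol.

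A reader might infer a definite loss of precision from replacing Visit 2 with an older rating. The documents do not support a figure. One simple model takes the variance ratio as (1 − r_s²)/(1 − r_b²), where r_b and r_s are the Visit 2 and Screening correlations with Week 6. It assumes that everyone doses on the Visit 2 date. Borrow 0.58 for r_b, although the plan gives that value only as a missing-data correlation. Set r_s to 0.58 times an assumed Screening-to-Visit 2 correlation. At 0.9 the ratio is (1 − 0.522²)/(1 − 0.58²) = 1.096; at 0.7, (1 − 0.406²)/0.6636 = 1.259; at 0.5, (1 − 0.29²)/0.6636 = 1.380. If Screening predicts Week 6 as well as Visit 2 does, the ratio is 1.000. The spread comes wholly from assumptions. The share of patients dosed on the Visit 2 date is also unknown, since Protocol 5.5 allows morning or evening dosing.

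A second objection is practical, and it holds: ordering events within Day 1 needs times. The documents do not say that rating and first-dose times are recorded for this purpose; Protocol 6.4 records dose times only around PK samples. Changing the wording alone would leave untimed same-day ratings unresolved.

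**Conclusion.** The conflict is real, and the efficacy baseline rule is wrong as written. Severity is minor. It affects only patients whose first dose is on the Visit 2 date (anywhere from none to all; the documents give no share), and only if SAP 9.0 is followed over Table 15-1. For them it moves three baselines to Screening, removes the HAM-A baseline, and can shift within-arm change and MADRS responder status.

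A reader might go further and infer that the primary comparison is biased or the trial's power misstated. The documents do not support either inference: both candidate baselines are pre-dose, and the planning calculation does not use the rule. That conclusion assumes that blinded patients in the three arms choose the day of their first dose in the same way. An effect on precision is possible, but no size can be given.

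SF-12 is also first administered at Visit 2. It is analysed as a health outcome in SAP 11.0, so the SAP 9.0 sentence may not govern it.

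**What to change.** 1. In SAP 9.0, delete *date of the*, so that baseline is the last non-missing assessment before the first dose of DB IP, as SAP 10.0 already has it for safety.
2. Add the same pre-dose condition to the Baseline row of Table 15-1. As it stands, the Day 1 window would also admit a rating made after the dose.
3. State as a required rule, not an option, that scheduled Visit 2 ratings without a recorded time count as pre-dose. Protocol 8.4.2 supports this by listing the ratings ahead of randomization and dispensing. Exclusion 6b supports it because the Visit 2 MADRS item 10 score decides eligibility.
4. Correct Protocol 7.3 in the same way, or record the departure in SAP 17.0.

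The cost is three words removed, one table condition, one convention and one line in the list of changes. No data collection, patient burden or sample size is affected. It should be settled before unblinding.

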Evaluate SAFER Score Qualification ^g		X					
Modified ATRQ	X						
HAMD-17	X	X				X	
YMRS	X	X				X	
MADRS	X	X	X	X	X	X	
CGI-S	X	X	X	X	X	X	
CGI-I			X	X	X	X	

Study Period	Screening	Baseline	Double-blind Treatment				Safety Follow-up
Visit	1	2	3	4	5	6/ET	7
Study Week	Up to -2^k	0	1	2	4	6^{a,b}	10
Study Day	Up to -14^k	1	8	15	29	43	71
Visit Windows		(within 14 days of start of screening procedures) ^k	± 3 Days	± 3 Days	± 3 Days	± 3 Days	± 3 Days
HAM-A		X		X		X	
SF-12		X				X	
BARS/AIMS/SAS		X	X	X	X	X	
C-SSRS	X	X	X	X	X	X	X
Adverse Events	X	X	X	X	X	X	X
Concomitant Medications	X	X	X	X	X	X	X
Dispense IP		X	X	X	X		
Drug Return and Compliance			X	X	X	X	
ADT Compliance		X	X	X	X	X	
Pharmacogenetic Consent ^h	X			X			
Pharmacogenetic Sample ⁱ				X			
Pharmacokinetic Sample ^j				X	X	X	

Note: After completion of Visit 6/ET, patients will be treated at the discretion of the investigator or designee.

ADT = antidepressant therapy; AIMS = Abnormal Involuntary Movement Scale; ATRQ = Antidepressant Treatment Response Questionnaire; BARS = Barnes Akathisia Rating Scale; CGI-I = Clinical Global Impressions—Improvement; CGI-S = Clinical Global Impressions—Severity; C-SSRS = Columbia—Suicide Severity Rating Scale; ET = early termination; HAM-A = Hamilton Anxiety Rating Scale; HAMD-17 = Hamilton Depression Rating Scale—17 items; IP = investigational product; MADRS = Montgomery-Åsberg Depression Rating Scale; SAS = Simpson-Angus Scale; SF-12 = Short Form-12 v2 Health Survey; YMRS = Young Mania Rating Scale.

^a Performed for all patients, including those prematurely discontinued after randomization (Visit 2).

^b Clinical findings upon termination must be followed until the condition returns to prestudy status or can be explained as unrelated to investigational product. If necessary, an additional follow-up visit should be scheduled.

^c Verified Clinical Trials database check to be performed, where applicable.

^d Clinical laboratory tests include hematology, serum chemistry, urinalysis (including urine myoglobin in patients with creatine phosphokinase levels > 1000 U/L or as clinically indicated for any rise in creatine phosphokinase levels or as necessitated by symptoms), as well as serum pregnancy test in women of childbearing potential.

^e Urine drug screen, blood alcohol concentration (by Breathalyzer), and serum pregnancy test can be repeated at random at request of investigator.

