8.4.4 Safety Follow-up (Visit 7)

The following procedures will be carried out at the Safety Follow-up Visit (Visit 7/Week 10):

- Review concomitant medications
- Collect vital signs measurements (including weight)
- Collect blood sample for serum pregnancy test (women of childbearing potential only)
- Review and assess AEs and SAEs
- Assess C-SSRS

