12.2.5 Visit 6/ET- End of Double-Blind and Early Termination Visit

Every attempt should be made to complete the Visit 6/ET efficacy, safety and health outcome assessments on the same date. In the event that a remote visit for Visit 6/ET is not possible at the scheduled timepoint, all Visit 6/ET efficacy assessments should be completed within 2 weeks of the last dose of IP. If Visit 6/ET is completed as a remote visit without the assessment of clinical laboratory parameters (including pregnancy testing, if applicable), physical examination and/or ECG, the patient should be brought back for safety assessments during the SFU period. Patients who have missed the safety assessments scheduled for Visit 6/ET and are unable to return for these assessments during the SFU period should be encouraged to return to the site for a final assessment of safety when possible. All attempts should be made to make a final assessment of safety even if it falls beyond the end of the Safety Follow-up period. If Visit 6/ET procedures are being completed more than 2 weeks after the last dose of IP, efficacy assessments should be omitted.

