The analysis population is defined to be the mITT population consisting of all randomized participants with ≥ 1 postbaseline assessment of the MADRS total score.

Variable

The variable is the primary efficacy endpoint, change from baseline to Week 6 in the MADRS total score.

Accounting of Intercurrent Events

Intercurrent events and their handling rules are described as follows:

- Regardless of whether allowed rescue medications are taken or not, data are included in the analysis. Participants are still taking assigned drugs as specified in the protocol while taking allowed rescue medications. The clinical objective is to assess the efficacy of the treatment regardless of allowed rescue medication use.
- To evaluate the efficacy at Week 6 in the mITT population, participants are assumed to adhere to the assigned treatment for the duration of the study. As a result, data after the discontinuation from the study treatment due to all reasons will not be included in the primary analysis and they will be assumed as missing at random.

Population-level Summary

The population-level summary for the primary endpoint is the difference in primary variable means between each cariprazine group and placebo.

To address the primary hypotheses that each dose of cariprazine is superior to placebo in the reduction of MADRS total score after 6 weeks of treatment, the change from baseline in MADRS total score will be analyzed using a mixed-effects model for repeated measures (MMRM) with treatment group, pooled country, ADT failure category (per CRF), visit, and treatment group-by-visit interaction as fixed effects, and the baseline value and baseline-by-visit interaction as the covariates. An unstructured covariance matrix will be used to model the covariance of within-participant scores. The Kenward-Roger approximation ([Kenward and Roger, 1997](#)) will be used to estimate denominator degrees of freedom. In the event of non-convergence of the model using unstructured covariance matrix, a structured covariance matrix will be used in combination with empirical variance estimate (i.e., sandwich estimator) to address the potential misspecified situation. The following sequence of alternative covariance structures (First-order ante-dependence [ANTE (1)], Toeplitz [TOEP], First-order autoregressive [AR (1)] and compound symmetry[CS]) will be considered in the MMRM until convergence.

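### Does SAP 9.1 have to define the date of treatment discontinuation before it drops later scores from the primary MMRM?

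*SAP*

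**What the plan says.** - **Exclusion rule.** SAP 9.1, under intercurrent events: "data after the discontinuation from the study treatment due to all reasons will not be included in the primary analysis". Protocol 7.3.1 says the same. SAP 9.2 analyses CGI-S, the key secondary endpoint, with a similar model.
- **Week 6 window.** Table 15-1 in SAP 15.1 defines it as "Days ≥ 36 and within Double-blind Treatment Period". The tie rule is: "If a participant has 2 or more visits within the same window, the last visit with a non-missing value will be used for analysis".
- **End of the double-blind period.** SAP 10.0, the safety section, ends it at the Visit 6 assessment or at early termination.
- **Last dose.** SAP 8.1 counts treatment duration up to and including the last double-blind dose. SAP 15.4 says how to fill in that date if it is missing. Protocol 8.8 requires it to be collected.
- **Off-drug ratings.** Footnote a of protocol Table 1, with protocol 8.8, requires the Visit 6/ET assessments, MADRS included, in patients who stop early. Visit 7 (protocol 8.4.4) has no MADRS.
- **COVID-19 attachment.** In protocol 12.2.5, if even a remote Visit 6/ET cannot be done on schedule, "all Visit 6/ET efficacy assessments should be completed within 2 weeks of the last dose of IP"; and "If Visit 6/ET procedures are being completed more than 2 weeks after the last dose of IP, efficacy assessments should be omitted".

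**The concern.** For someone who stops early, the ET rating is the last scheduled MADRS, so it is normally the only score the exclusion can touch. If discontinuation is dated at the ET visit, nothing scheduled is removed. If it is dated at the last dose, every later ET score goes. A two-week limit borrowed from protocol 12.2.5 falls between the two. Table 15-1 labels by study day, so an off-drug ET score on Day 36 or later would be called Week 6 unless it has already been removed.

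The choice also reaches CGI-S and the sensitivity analyses. Pattern-mixture patterns are set by the last observed visit, and the copy-reference analysis imputes what is missing after discontinuation. A lack-of-efficacy dropout whose ET score counted as Week 6 would not be imputed. Because this sentence is the estimand's whole rule for stopping treatment, discretion over it after unblinding would be unwelcome.

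**Working it through.** **1. Does the choice of date matter?** Week 6 value for four illustrative participants under each candidate date:

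| Participant | Last dose | ET visit | Last dose + 14 days |
|---|---|---|---|
| Last dose Day 22, ET Day 36 | missing | Day 36 | Day 36 |
| Last dose Day 30, ET Day 38 | missing | Day 38 | Day 38 |
| Last dose Day 28, ET Day 45 | missing | Day 45 | missing |
| Completer, last dose Day 42, Visit 6 Day 43 | Day 43* | Day 43 | Day 43 |

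*A program that applied a last-dose cut to everyone would lose this score. SAP 9.1 applies only after discontinuation, and a completer has not discontinued.

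So the dates are not interchangeable.

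**2. Which date do the texts support?** Dating by the ET visit would leave the SAP 9.1 sentence with no scheduled score to act on, and a reading that empties a rule is a poor one. SAP 10.0 sets a safety reporting period. Protocol 12.2.5 limits when efficacy is collected in COVID-affected cases. Neither is offered as the date of discontinuation. Last dose is what SAP 8.1 and 15.4 already use for the end of treatment.

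**3. Does the order matter?** Visit 5 is due on Day 29 ± 3, so no later than Day 32, and the Week 6 window opens on Day 36. Order can change Week 6 only when two ratings fall on Day 36 or later. That takes the COVID extension (Day 29 + 7 = Day 36) or an unscheduled rating. Example: Visit 5 on Day 36, last dose Day 37, ET Day 41. Excluding first gives Week 6 = Day 36; windowing first gives missing. Week 4 can be affected more easily: with Visit 5 on Day 29, last dose Day 31 and ET Day 34, excluding first keeps Day 29 and windowing first loses Week 4. Since SAP 9.1 takes the data out of the analysis, an excluded score should not compete for a window, so excluding first is the ordinary reading.

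**4. The plan's power figure.** Inputs from SAP 13.0 and 9.2: 250 per arm, effect size 0.286, dropout 15%, correlation 0.58, one-sided alpha 0.025, truncation parameter 0.9. Taking the information loss as 0.15 × (1 − 0.58²), effective n = 250 × (1 − 0.15 × 0.6636) = 225.1 per arm. The mean of each z-statistic is 0.286 × √(225.1/2) = 3.03, and the two comparisons have correlation 0.5. Truncated Hochberg without the re-testing step gives 83.7% per dose and 91.1% for at least one dose (SAP: 83% and 90%). Regular Hochberg gives 84.1% per dose (protocol 7.7: 84%).

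**5. How many records?** Dropouts: 0.15 × 750 = 112.5; completers: 637.5. Assumptions not in the documents: stop dates evenly spread, and every dropout has an off-drug ET score.

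- ET the day after last dose (Days 2–42): 7 of 41 days fall in Week 6; 112.5 × 7/41 = 19.2 records, 3.0% of 637.5.
- ET always 14 days after last dose: last-dose Days 22–41 qualify, 20 of 41; 112.5 × 20/41 = 54.9 records, 8.6%. This is an upper limit, because protocol 12.2.5 covers only COVID-affected visits.

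**6. Effect on power if those scores are kept.** Let s be the share of dropouts with such a score and r the share of the drug effect it still carries. Effect = 0.286 × (1 − 0.15 × s × (1 − r)); effective n = 250 × (1 − 0.15 × (1 − s) × 0.6636).

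| s | n | r = 0 | r = 0.5 | r = 1 |
|---|---|---|---|---|
| 0 (all excluded) | 225.1 | 83.7% | 83.7% | 83.7% |
| 7/41 | 229.4 | 82.4% | 83.4% | 84.4% |
| 20/41 | 237.3 | 79.6% | 82.8% | 85.7% |

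The first scenario moves power by −1.3 to +0.7 points, the upper limit by −4.1 to +2.0. At r = 0.5 the changes are −0.3 and −0.9.

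**The case for a change.** The strongest argument for amending is that a programmer can follow SAP 15.1 and SAP 10.0 to the letter and keep off-drug ET scores as Week 6, while another follows SAP 9.1 by last dose and drops them. Table 15-1 is headed for efficacy as well as safety and refers to the double-blind period, and SAP 10.0 is the only section that says how that period ends for someone who terminates early. Naming the date would cost a sentence, and the dates are already collected.

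Part of this stands: the SAP does not name the date or the order, and one sentence would do no harm. But a window table only labels the data that are in the analysis; it does not readmit data the estimand has removed. Going further means choices the documents do not settle. One candidate is a three-day tolerance taken from the missed-dose rule in protocol 5.6.1. That rule governs withdrawal and does not say when a score becomes post-treatment; for COVID-related gaps protocol 12.2.6 allows up to 7 missed doses; and the tolerance would keep all 19 records of the first scenario, where ET is one day after last dose. Whether to have a tolerance, and whether to add a supportive model with the excluded scores, are matters on which statisticians can reasonably differ.

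**Conclusion.** No change is needed. This is missing detail that an analyst fills sensibly: date discontinuation by the last double-blind dose, apply the exclusion only to participants who discontinue, and apply it before windowing. That reading keeps completers' Visit 6 scores, carries over to CGI-S, and leaves the pattern-mixture and copy-reference analyses working from one consistent data set. SAP 3.0 also places table specifications in a separate document, not available here, where such a rule may already be set.

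The likely effect is about one power point per dose or less, in either direction, outside the COVID limit. That rests on the assumed spread of stop dates and ET intervals, and on off-drug scores keeping some of the drug effect. The Amendment 1 summary in protocol 12.4 mentions a long half-life, which makes r = 0 unlikely shortly after the last dose, but gives no value. The direction and size of any shift in the treatment estimate itself cannot be computed from the documents.
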